Patients with a clinical diagnosis of ruptured AAA will be individually randomized, in either Accident & Emergency or the vascular reception unit, to either a strategy of preferential endovascular repair (n=300) or normal care with open repair (n=300). The strategy of endovascular repair necessitates rapid access to CT angiography to confirm rupture and determine anatomical suitability for endovascular repair. The majority (55-66%) of patients with ruptured AAA will be considered anatomically suitable for endovascular repair and then receive this treatment. Remaining patients with ruptured AAA will undergo open repair (Figure 1). All patients will be followed for a minimum of 3 years for major morbidities, health service costs and mortality. After consultation with patients and their families (who unanimously viewed coming home alive as the most important consideration), we have retained in-hospital mortality as a key outcome, but in line with recommendations from the Board have altered our primary outcome measure to 30-day mortality.

Outcome measures

Primary: 30-day mortality

Secondary: 24-hour, in-hospital, and 1-year mortality, time from admission to AAA repair, complications and reinterventions related to ruptured AAA repair in 1 year, other major morbidity (stroke, myocardial infarction, renal or respiratory failure) in 1 year, diagnostic accuracy, patient disposal, costs and cost-effectiveness. 3-year costeffectiveness analysis will also be undertaken, (with a formal request for trial extension).

Planned interventions

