Our strategy for eEVAR is the novel intervention. This involves urgent CT angiography to confirm the diagnosis and plan endovascular repair whenever feasible: endovascular supracoeliac aortic balloon occlusion will be used to support less stable patients. Guidelines for anatomical restrictions to endovascular repair are given in Appendix II. Patients will then be transferred to the intervention suite or operating theatre. For those in whom aortic anatomy precludes endovascular repair, open repair will be performed. A minority of patients (~5%) will not have an AAA identified on CT scan, although another diagnosis may be indicated: these patients will be directed to appropriate care. Most of the endovascular interventions will involve an aorto-uni-iliac graft with subsequent femoro-femoral cross-over graft, with contralateral iliac occlusion. Interventional control of the aorta can be achieved using local/regional anaesthesia, with general anaesthesia being used later in the procedure as necessary. A few patients will not require a critical care bed post-operatively. The core laboratory will assess the technical success of the procedure from the post-operative CT scan, 3 months after intervention.

The control intervention is the standard current practice of open repair, with most patients, including all the less haemodynamically stable patients, being taken directly to the operating theatre for laparotomy and open repair without confirmation of ruptured AAA by diagnostic imaging (although AAA may have been confirmed by ultrasonography). Aneurysms will be repaired by cross-clamping the proximal aorta and then inserting a prosthetic inlay graft. The very stable patients may undergo diagnostic imaging before laparotomy. At laparotomy a minority of patients will not have ruptured aneurysm, some may have AAA without rupture and some may have no aneurysm. All laparotomies will be conducted under general anaesthesia and patients will require a critical care bed post-operatively. There will be no requirement for post-operative CT scan unless this is indicated clinically.

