Both experimental (endovascular) and control (open surgery) interventions will follow an integrated care pathway from ambulance through Accident & Emergency, based on the JRCALC 2006 guidelines for abdominal trauma [19], see Appendix II. These guidelines limit fluid resuscitation in conscious patients with a palpable radial pulse with permissive hypotension (70-80 mm Hg). Physiological viability will be calculated for all patients using the Hardman index [20]. Guidelines will be provided for anaesthetic and critical care (Appendix II). Post-operatively statins will be recommended for all patients.

Frequency and duration of follow-up

All patients with ruptured AAA will be reviewed as an outpatient at 3 months (if they have been discharged) and again at 1 year after aortic repair. EQ-5D questionnaires for quality of life will be administered at 3 months, 1 year and again mid-term (between 2.5 and 4 years) after AAA repair. Patients with endovascular repair will require one post-operative CT scan (at 3 months after repair) and then the local follow-up for patients with endografts, usually requiring either CT or duplex scan at 6 months and 1 year. During the first year information also will be collected on complications and interventions relating to ruptured aneurysm repair as well as major morbidities (e.g. myocardial infarction, stroke, renal failure & dialysis) or hospitalizations from other causes. All randomised patients, with or without rAAA will be flagged with NHS Information Centre for cause and date of death, based on the pre-operative consent (conditional NIGB approval shown in Appendix IV).

Arrangements for randomization

Randomisation will be available at all times (24/7) by either telephone or internet using the services of thesealedenvelope.com: randomisation will be stratified by site and gender. For every patient randomized to normal care (open repair), 1 patient will be randomized to a strategy of endovascular repair. Randomisation will use a variable block size. This is a surgical trial of conventional versus a strategy of minimally invasive surgery, so patients & carers cannot be blinded to treatment allocation.

Inclusion and exclusion criteria

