Patients have provided consent for review of their routine clinical data for up to 5 years and for quality of life assessments at 3 and 12 months following randomization. They have not formally given signed consent for a mid-term quality of life assessment but the Chairman of the lead Research Ethics Committee for the trial has proposed that return of the mid-term quality of life assessment would imply consent.

Trial documentation

This will be kept securely at Imperial College (duplicate database at the University of Cambridge) for at least 15 years after completion of the trial.

Planned analyses

The analyses will be carried out according to a detailed plan drawn up before the outcome data are inspected. A CONSORT diagram will describe the patient flow and exclusions. The groups will be considered as randomised (intention to treat) as a test of the interventional policy. The primary outcome is 30-day mortality, with secondary outcomes of 24-hour, in-hospital and 1-year mortality; each will be compared with a chi squared test, and the

estimated difference in proportions accompanied by a confidence interval. Adjustment for the baseline Hardman index will be undertaken in secondary analyses using logistic regression. Time to complications, re-interventions, and major morbidities after repair of ruptured aneurysm will be compared using the log-rank test and Cox regression.

Cost-effectiveness analysis will report the mean (95% CI) incremental costs and QALYs of eEVAR versus open repair at one year, and the probability that eEVAR is cost-effective compared to open repair, at different levels of willingness to pay for a QALY gained. The analysis will address issues posed by missing EQ-5D or cost data [32] and censoring [33]. Survival analysis will be used to extrapolate any within-trial differences in costs and QALYs to project lifetime cost-effectiveness [34,35]. Sensitivity analysis will test whether the results are robust to methodological assumptions. The effect of the algorithm of care on the outcome of open surgery will be reviewed against national statistics. The statistical analysis plans will be published on the trial website before any analysis commences.

Subgroup analyses

A limited number of predefined subgroups will be compared using tests of interaction, only for the primary outcome (in-hospital mortality), using logistic regression. Subgroups will be defined by age (continuous), gender, and Hardman index (continuous).

Frequency of analyses

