2 Contrast enhanced scan to be taken from the level of the diaphragmatic hiatus to lower border of femoral heads. The scan must be performed during the arterial phase of contrast enhancement. The exact protocol will depend on the scanner available and the individual department but a contrast dose of 100ml given at 3-4ml/second is recommended. The notional slice thickness should be 1-2mm. When a scan already was performed at another hospital, the patient is to transfer to the trial centre with a CD copy of the scan (DICOM data). Ideally 2 copies will be provided, one for the trial core lab. *Randomisation must occur before review of the CT scan provided*. Repeat CT scans should be avoided.

3 All CT scans must be reviewed by the interventional team for diagnosis and measurement.

4 Definition of rupture is intraperitoneal or retroperitoneal blood seen outside the aneurysm sac.

5 Anonymised CD containing DICOM data of the scan to be sent to the trial centre for core laboratory analysis.

Assessment of suitability for eEVAR

The proposed trial is pragmatic and it is therefore not possible to set exact criteria for anatomical suitability for endovascular repair of ruptured AAA. The criteria will vary to a marginal degree from centre to centre and will be based on experience, type of graft preferred, the configuration of graft, the development of new technologies and other local factors. In general, the anatomic considerations are similar to those for elective procedures and proximal neck morphology with a diameter exceeding 32mm or a length less that 10mm may be considered unfavorable, although there will be no absolute requirements set for the proposed study. Iliac artery diameters should be in the range 8-22mm.

Technical assessment of procedure success

One contrast enhance dual phase (arterial and venous) scan should be performed 3 months post implant. Scan volume should be from the diaphragms to the lower border of the femoral heads. A CD of the DICOM data should be sent to the core lab for analysis.

3 Protocol for eEVAR implantation

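### Scheduled scans follow endovascular repair but not open repair, so the 1-year time-to-complication comparison can count imaging-only findings almost only in the endovascular-strategy arm

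*Protocol*

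**What the plan says.** The follow-up schedules are set in section 3 of the Protocol.

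- **After endovascular repair.** Frequency and duration of follow-up makes one CT at 3 months a requirement. Local endograft follow-up comes after it, "usually requiring either CT or duplex scan at 6 months and 1 year". Appendix II (Technical assessment of procedure success) repeats the first scan: "One contrast enhance dual phase (arterial and venous) scan should be performed 3 months post implant". It is read by the core laboratory.
- **After open repair.** Planned interventions states: "There will be no requirement for post-operative CT scan unless this is indicated clinically".
- **Common to both.** "All patients with ruptured AAA will be reviewed as an outpatient at 3 months (if they have been discharged) and again at 1 year" after repair.

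Outcome measures lists among the secondary outcomes "complications and reinterventions related to ruptured AAA repair in 1 year". Planned analyses says: "Time to complications, re-interventions, and major morbidities after repair of ruptured aneurysm will be compared using the log-rank test and Cox regression". On the analysis population it says: "The groups will be considered as randomised (intention to treat) as a test of the interventional policy".

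The Protocol does not limit complications to symptomatic events and does not ask how an event was found. It makes no allowance for the different amount of imaging.

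**The concern.** A complication that causes no symptoms can enter the data only if someone looks for it. Endograft patients are looked at about three times in the first year by schedule, and open-repair patients not at all. If the two strategies carried the same true risk, the strategy arm would still show more complications. Some would be dated at or near 3, 6 and 12 months because that is when the scans happen, which also shapes the hazards that the Cox model compares.

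At stake is the interpretation of a named secondary outcome. If the strategy arm shows more complications, the planned analysis cannot tell worse outcomes from more looking. How an event came to light is best recorded when it is reported, since it may not be recoverable later.

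**Working it through.** The Protocol gives no event rate, hazard ratio or power for complications, so there is no stated figure to reproduce for this outcome. The imaged share can be built from the planning rates in Proposed sample size.

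**Inputs from the Protocol.** 300 patients per arm; 55% suitable for endovascular repair; 5% without rupture; 30-day mortality 47% after open and 21% after endovascular repair.

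**Check of how the 55% is applied.** Open arm: 0.95 × 47% = 44.65%. Strategy arm: 0.55 × 21% + 0.40 × 47% = 30.35%. These match the stated 44.6% and 30.4%, so the plan divides the strategy arm into 55% endovascular, 40% open and 5% without rupture.

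**Imaged share f of strategy-arm ruptures**
- Counted at randomisation: 55/95 = 57.9%.
- Counting only endograft patients alive at 30 days: 300 × 0.55 × 0.79 = 130 of 285 ruptures, or 45.7%. No more than these can reach the 3-month scan.
- Open arm: 0% imaged on schedule.

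**First illustration.** Let the true complication risk r be equal in both arms, and let a share s of complications be silent unless scanned. The value of s is assumed.
- Observed risk, strategy arm: r × [f + (1 − f)(1 − s)]
- Observed risk, open arm: r × (1 − s)
- Ratio: 1 + f × s/(1 − s), whatever the value of r

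| Silent share s (assumed) | Ratio, f = 57.9% | Ratio, f = 45.7% |
|---|---|---|
| 5% | 1.03 | 1.02 |
| 10% | 1.06 | 1.05 |
| 20% | 1.14 | 1.11 |
| 40% | 1.39 | 1.30 |

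**Second illustration, confined to repaired patients alive at 30 days.** The strategy arm has 130 endograft survivors plus 300 × 0.40 × 0.53 = 64 open-repair survivors, so 130/194 = 67% are imaged on schedule. The open arm has 300 × 0.95 × 0.53 = 151 survivors, none imaged on schedule. Assume a 15% clinical event rate at 1 year in both arms, and that imaging alone adds a counted event in a share q of scanned patients.
- Strategy-arm risk: 0.15 + 0.85 × 0.672 × q
- Apparent hazard ratio: ln(1 − strategy-arm risk)/ln(0.85)

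| q (assumed) | Apparent hazard ratio | Chance of a significant result against the strategy arm (Schoenfeld) |
|---|---|---|
| 2% | 1.08 | 5% |
| 5% | 1.21 | 11% |
| 10% | 1.43 | 29% |
| 20% | 1.89 | 77% |

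Both models point the same way. The effect is negligible when silent findings are rare and material when they are common.

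**The case against.** The strongest reply is that surveillance belongs to the endovascular policy and the trial tests that policy as randomised. A reintervention prompted by a scheduled scan happens to the patient and costs money, and section 7 (Treatment costs) already expects higher reintervention costs after endovascular repair. Removing such procedures would delete real events from one arm only and tilt the result towards endovascular repair. This stands, and it limits the point to complications known only from imaging.

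A reader might go further and infer that an excess of complications, or the cost difference it feeds, could be nothing but detection. The documents do not support that for reinterventions or costs, which are genuinely incurred. Nor do they support reading Planned analyses as pooling all complications into one endpoint. That section names complications, reinterventions and major morbidities, describes no composite, and does not say that symptom-free scan findings count.

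Two further objections hold in part. The silent share has no source in the documents. Because the first scheduled scan is at 3 months, complications that declare themselves during the index admission are counted in both arms, so the share may be small. Also, the definition of a complication is commonly left to the statistical analysis plan, which is not shown and may be narrower. But the Protocol itself fixes both the unequal imaging and the direct comparison. Imaging follows the treatment received, so strategy-arm patients who have open repair are not scanned on schedule either. That dilutes the bias but does not remove it.

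**Conclusion.** The point holds for one secondary outcome, complications within 1 year, and its direction is clear: scheduled imaging can only add counted events or bring them forward, and almost only in the endovascular-strategy arm. All mortality outcomes are untouched, and overt morbidities such as stroke, myocardial infarction and dialysis are little affected.

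The size cannot be derived from the documents. With no true difference, the observed risk ratio runs from about 1.02 to 1.39 over silent shares of 5% to 40% and imaged shares of 46% to 58%. This assumes equal true risk and an equal silent share for two different repairs. The survivor-based hazard ratios rest on the assumed 15% event rate and the assumed yield of imaging. The figures show when the bias would matter; they do not predict it. The change is worth making because it is cheap and because without it an excess of complications could not be interpreted.

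**What to change.** 1. Record for each complication and reintervention whether it was triggered by symptoms or clinical indication, or by scheduled imaging.
2. Keep the as-randomised all-event comparison, with all reinterventions and their costs included.
3. Add beside it a log-rank and Cox comparison restricted to clinically triggered complications.
4. Tabulate by arm the imaging-only complications and the reinterventions they prompted.

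The cost is one case-record field, one added comparison and one table, with no extra scans or staff and no change in care. The added comparison has fewer events. Classifying the trigger also takes some judgement by people who know the treatment, so it can itself be biased, which is a further reason to keep the all-event comparison alongside.

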IMPROVE Can eEVAR reduce mortality from ruptured AAA?

PROTOCOL

[name] & 12 co-applicants

1 Can emergency endovascular aneurysm repair (eEVAR) improve the survival from ruptured abdominal aortic aneurysm?

2 How the project has changed since the outline proposal and initial full proposal

The outline proposal was for a cluster trial at the level of the ambulance service to be followed by in hospital randomisation of patients with clinical diagnosis of ruptured abdominal aortic aneurysm (AAA) to either a strategy of endovascular aneurysm repair or to normal care with open repair. The Board requested that a full proposal focus on a Randomised Controlled Trial for open repair against endovascular repair only. We have followed this guidance. Since the outline proposal there have been 2 systematic reviews of the topic and a Cochrane review, all lamenting the lack of randomised trial data for endovascular versus open repair of ruptured AAA. The best quality review reported on the outcome of in-hospital mortality. We have consulted widely, including with patients to seek their views on trial design and relevant outcome measures: in-hospital mortality was more important to patients and their families than was 30-day mortality. However, the Emergency Care Board was keen for us to retain 30d mortality as the primary outcome: the Board also has recommended a 1:1 randomisation rather than the 2:1 randomisation we had considered. We also have been able to base the percentage of patients anatomically suitable for endovascular repair on the systematic review data and access unpublished data from a pilot trial in Nottingham to indicate the percentage of patients with a hospital clinical diagnosis of ruptured AAA who do not have an aneurysm. Based on these changes, we still need a large trial of about 600 patients and therefore have an extended recruitment period (by 12 months). The costs of the trial have been revised in line with these changes and other suggestions from the Board.

3 Planned investigation

Background

Without intervention ruptured AAA is fatal and the overall mortality exceeds 85%. About half of patients with ruptured aneurysms die in the community. Half of those patients arriving in Accident & Emergency do not reach the operating theatre alive. Among the patients who reach the operating theatre (for open surgical repair under general anaesthesia), only half will leave hospital alive. These stark figures have changed little over the last 50 years [1].

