The trial will include all non-moribund patients with a clinical diagnosis of suspected ruptured AAA in Accident & Emergency. This will include patients transferred from other hospitals with a diagnostic CT scan, with patients to be randomised before suitability for endovascular repair is assessed. There will be no formal age limits.

Patients with known connective tissue disorders (eg Marfan syndrome), with known previous elective AAA repair, rupture of an isolated iliac aneurysm and with aorto-caval or aorto-enteric fistulae will be excluded. Deeply unconscious patients, very ill patients not able to survive CT-scanning and those previously assessed for elective EVAR will be excluded.

Proposed sample size

We will randomise 600 patients, half to immediate open repair and half to CT scan followed by eEVAR if anatomically suitable and open repair if not anatomically suitable. **The trial, comparing the groups as randomised, would have 90% power to detect (as significant at 5%) a difference in mortality of 14%.** This is based on estimated 30-day mortalities of 47% and 21% for patients receiving open repair and endovascular repair respectively, an estimate of 55% of patients being anatomically suitable for eEVAR after CT scan and that 5% of both randomized groups will not have ruptured AAA (identified only after randomisation, 5% figure taken from unpublished data of the pilot Nottingham trial). The estimated mortality is 44.6% in the open repair group and 30.4% in the EVAR first strategy group.

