Patient compliance is not an issue in a trial of emergency intervention. Patients will be flagged with the Health and Social Care Information Centre (previously NHS Information Centre) to ensure that post-discharge mortality data can be obtained: this includes patients who are subsequently identified as not having a ruptured AAA. After discharge, the trial will only actively follow-up patients with a confirmed diagnosis of rAAA for hospital and health economic data. It is anticipated that a minority of these (10%) will not attend for 1 year follow up, based on observations from the EVAR trials [15,16]. The ED-5Q questionnaire can be mailed to such patients not attending for 3m or 1 year follow ups. One later EQ-5D questionnaire at between 2.5 and 4 years after randomization will support mid-term cost-effectiveness evaluation: questionnaires will be mailed to surviving patients on a quarterly basis, immediately after the regular update of death reporting for the trial from Data Linkage and Extract Service.

Cost measurement

Microcosting methods will be used to record the costs associated with either intervention. Detailed information will be collected on the surgery undertaken for both patient groups including the stents used, time in theatre, use of blood products, contrast agents and endografts. All post operative interventions will be recorded, together with the days in hospital (critical care, general medical wards). These resource use data will be combined with appropriate unit costs. Previously collected detailed unit costs will be available (EVAR 1 and 2 trials), which will be updated during site visits to individual trust finance departments, and supplemented by unit costs from the NHS *Payment by results* databases. The impact of the surgical method on subsequent morbidity costs will be assessed. Each day in critical care will be assigned to a health care resource group (HRG) using mandated data collected for the critical care minimum dataset (CCMDS). These activity data will be combined with unit cost per hospital bed-day (by HRG) from the NHS *Payment by results* database. Readmissions will be recorded. The use of personal health services will be recorded by adapting previously developed questionnaires [27], and administering them at one year post randomisation. Community service use will then be valued using unit costs taken from published sources [28].

Number of centres involved – 30 includes Royal Free

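### The 90% power does not follow from the printed inputs (these give about 95%), and the calculation makes no stated allowance for deaths before repair, crossover or unruptured aneurysms

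*Protocol*

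**What the plan says.** The Protocol section *Proposed sample size* states: "We will randomise 600 patients, half to immediate open repair and half to CT scan followed by eEVAR if anatomically suitable", with open repair for those not suitable. The trial, compared as randomised, "would have 90% power to detect (as significant at 5%) a difference in mortality of 14" percentage points. The inputs follow: "This is based on estimated 30-day mortalities of 47% and 21% for patients receiving open repair and endovascular repair respectively", 55% anatomically suitable after CT, and 5% of each group without ruptured AAA (from unpublished Nottingham pilot data). The resulting mortalities are 44.6% (open) and 30.4% (EVAR first).

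Other sections bear on these inputs:

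- *Background* gives 47-8% as the mortality of open surgical repairs performed.
- *The proposed trial* says patients "will be individually randomized, in either Accident & Emergency or the vascular reception unit", that is, before any repair.
- Section 2 says the Nottingham data supply the percentage with no aneurysm. *Planned interventions* says "A minority of patients (~5%) will not have an AAA identified on CT scan" and, for the open arm, expects some patients with an unruptured AAA and some with no aneurysm.
- The text after the sample size paragraph gives reasons why the estimates may be conservative, including suitability of 67% overall and 70-80% in some centres. It names no factor that works in the other direction.

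**The concern.** The mortalities belong to patients who received a repair, but the comparison is between patients randomised earlier. Ruptured patients who die or are turned down before repair, suitable patients who receive the other arm's operation, and patients with an unruptured aneurysm contribute little or no treatment contrast. Each therefore shrinks the as-randomised difference, and the calculation allows for none of the first two and only part of the third.

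The 5% is a separate difficulty that needs no assumed rate. One figure is used for two quantities, no aneurysm and no rupture, and the second should be larger if unruptured aneurysms also occur.

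The power statement is what a reader will use to judge an inconclusive result, so it should follow from its inputs and show what it depends on.

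**Working it through.** **Inputs.** From *Proposed sample size*: mortality 0.47 (open) and 0.21 (endovascular), suitability 0.55, no rupture 0.05, 300 per arm, 5% significance. Sidedness is not stated; two-sided is assumed. The rates of pre-repair death, crossover and higher non-rupture used below are assumptions, because the Protocol gives none for randomised patients.

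**Step 1: reproduce the arm mortalities.**

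- Open: 0.95 × 0.47 = 44.65%.
- EVAR first: 0.55 × 0.21 + 0.40 × 0.47 = 11.55% + 18.80% = 30.35%.

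These match the printed 44.6% and 30.4%. They do so only if every ruptured patient is repaired, every suitable patient in the strategy arm receives eEVAR, no control does, and non-ruptures have no deaths. They also take 55% as a share of all randomised. If 55% is a share of ruptured patients, the EVAR-first rate is 0.95 × (0.55 × 0.21 + 0.45 × 0.47) = 31.1%.

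**Step 2: reproduce the power.** Two proportions, pooled variance under the null, mean rate 0.375:

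z = (√300 × 0.142 − 1.96 × √(2 × 0.375 × 0.625)) / √(0.446 × 0.554 + 0.304 × 0.696) = (2.460 − 1.342) / 0.677 = 1.65

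Power is Φ(1.65) = 95.1% (94.1% with continuity correction). A difference of exactly 14 points (44.6% v 30.6%) gives 94.5%. Only 486 patients are needed for 90% at the printed rates; 600 is the number for 95%. With 55% as a share of ruptures, power is 93.1% (91.9% with continuity correction). None of these is 90%.

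**Step 3: add dilution.** Let r = share without rupture (mortality taken as 0), d = share of ruptured patients dying without repair, s = suitable share of ruptures, c = suitable strategy-arm patients given open repair, c₂ = suitable open-arm patients given eEVAR.

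- Open = (1−r)[d + (1−d)(0.47 − c₂ × s × 0.26)]
- EVAR first = (1−r)[d + (1−d)(0.47 − s(1−c) × 0.26)]

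Setting s = 0.55/0.95 = 0.579 reproduces 30.35%. Example with d = 10%: open = 0.95 × (0.10 + 0.90 × 0.47) = 49.7%; EVAR first = 0.95 × (0.10 + 0.90 × 0.3195) = 36.8%; difference 12.9 points, power 89.1%.

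| Assumed change | Open v EVAR first | Power, printed basis | Power, 55% of ruptures |
|---|---|---|---|
| None | 44.65 v 30.35 | 95.3% | 93.1% |
| 5% pre-repair death | 47.2 v 33.6 | 92.6% | 89.8% |
| 10% pre-repair death | 49.7 v 36.8 | 89.1% | 85.7% |
| 20% pre-repair death | 54.7 v 43.3 | 80.2% | 76.0% |
| 5% crossover each way | 43.9 v 31.1 | 90.4% | 87.2% |
| 10% crossover each way | 43.2 v 31.8 | 82.7% | 78.5% |
| 10% without rupture | 42.3 v 28.8 | 93.6% | 91.0% |
| 20% without rupture | 37.6 v 25.6 | 88.9% | 85.4% |
| 5% pre-repair death + 5% crossover each way | 46.5 v 34.3 | 86.4% | 82.7% |
| The same + 10% without rupture | 44.0 v 32.5 | 83.3% | 79.2% |

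The mortalities shown are on the printed basis. The first row uses unrounded rates, hence 95.3% rather than 95.1%.

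**Step 4: the other direction.** With 67% of ruptures suitable and no dilution, the difference is 0.95 × 0.67 × 0.26 = 16.5 points and power is 98.9%. With 67% suitable plus 5% pre-repair death, 5% crossover each way and 10% without rupture, power is still 92.6%.

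**The case against.** The strongest reply is that the plan already carries a margin. Its printed rates give about 95%, so 90% is an understatement that may have been meant to cover dilution. Higher suitability, which the Protocol documents, could more than offset moderate dilution. This stands as far as it goes: at 600 patients and 44.6% in controls, 90% power holds down to a difference of about 12.8 points. But the Protocol does not say that the gap between 95% and 90% is an allowance, or for what.

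Two further points stand in part. The Protocol says the open mortality probably already includes some contained ruptures and unruptured aneurysms, so raising the non-rupture share while keeping 47% counts some of them twice. *Planned analyses* already fixes analysis as randomised and a CONSORT flow diagram, so untreated and crossed-over patients will be visible and kept in their groups.

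Several stronger readings are tempting, and the document does not support them:

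- **That the trial is underpowered.** This requires rates the Protocol does not give.
- **That half of randomised patients die before repair.** *Background* says "Half of those patients arriving in Accident & Emergency do not reach the operating theatre alive", but this concerns unselected arrivals. The trial excludes moribund and deeply unconscious patients and those unable to survive CT.
- **That limited interventional radiology proves crossover.** The section on generalisability gives it as a reason for not randomising patients, and centres must be able to perform EVAR at all hours.
- **That "Patient compliance is not an issue in a trial of emergency intervention" denies crossover.** The sentence is about patients, and it opens a paragraph on follow-up.

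**Conclusion.** The point holds as a fault in how the power is derived and stated; it does not show that 600 patients are too few. Two parts rest on the document alone. The stated 90% does not follow from 44.6% v 30.4% with 300 per arm, which gives about 95% two-sided. And the 5% is labelled as no aneurysm in two places and as no rupture in the calculation. We cannot tell which label is right, because the source is unpublished.

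The size of any loss is conditional. On the printed basis a single dilution of about 5% leaves power at or above 90%, and moderate combinations take it to about 83-86%. If 55% is a share of ruptures, the margin is smaller: 5% pre-repair death alone gives 89.8%. Suitability near 67% would restore power above 90% in the combined scenario shown.

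**What to change.** Keep 600 patients and revise the text of *Proposed sample size*:

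1. Restate the power from the printed rates, about 95% before dilution, and give the sidedness.
2. Say whether 55% is a share of all randomised or of ruptured patients. If of ruptured patients, the EVAR-first rate becomes 31.1% and power 93%.
3. Reconcile the 5% across section 2, *Planned interventions* and the sample size paragraph as no aneurysm or no rupture. If it means no aneurysm, add an assumed share for unruptured AAA and say how much of that is already inside the 47%.
4. Beside the reasons for conservatism, add a short table of power over pre-repair death or no repair (0, 5, 10, 20%), crossover (0, 5, 10%), non-rupture (5, 10, 15%) and suitability (55-70%), so that it runs in both directions.

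The cost is text only, with no change to patients, analysis or conduct. The downside is that the power statement becomes conditional, and less favourable in some scenarios.
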